7.3.5 EARLY TERMINATION VISIT

If the participant chooses to terminate participation early, he or she will be contacted either in person or by phone to verify the decision to discontinue participation. This decision will be documented by research personnel.

7.4 SCHEDULE OF EVENTS TABLE

	Screening & Enrollment	Prior to RT	During Radiation Therapy (RT)							Post-RT
	Baseline	CT Simulation Visit	Week 1	Week 2	Week 3	Week 4	Week 5	Week 6	Week 7	Week 12
Consent	X									
Eligibility ¹	X									
Demographics	X									
Randomization ²	X									
CT Simulation		X								
In-Person or virtual GI Session		X	X							
Patient self-administered GI use ³			X	X	X	X	X	X	X	
Anxiety HADS-A	X		X		X				X	X
Depression HADS-D	X		X		X				X	X
Symptoms MSAS-SF	X				X				X	X
Health-related QOL FACT-HN	X				X				X	X
Intervention use TLFB-I ³		X	X	X	X	X	X	X	X	
Anxiolytic use TLFB-A		X	X	X	X	X	X	X	X	
Research Assistant Contact for F/U ⁴										X
Qualitative Interview ⁵										X

*Patients may complete the assessments for weeks 1, 3, 7 and 12, listed above any time during the specified week (7 days) of treatment, with Day 1 being defined as the first day of radiation treatment. TLFB measures may be completed at any time.

1. Determined by chart review and confirmation of eligibility between research study personnel and treating physician.
2. Upon completion of baseline measures.
3. Guided imagery (intervention) participants only.
4. Following completion of 12-week study measures, in person or on the phone:
Treatment as usual participants will be provided with an MP3 player containing the guided imagery audio files either in person or by mail.
Intervention participants will be offered the opportunity to participate in a 30-minute qualitative interview assessing the acceptability and feasibility of the intervention.
5. The qualitative interview may be conducted via phone or in person following completion of the Week 12 study assessments.

7.5 CONCOMITANT MEDICATIONS, TREATMENTS, AND PROCEDURES

All prescription medications related to the study aims taken during study participation will be recorded in the study database. For this protocol, relevant prescription medications include anxiolytic medication (i.e., alprazolam, bromazepam, chlordiazepoxide, clonazepam, clorazepate, diazepam, flurazepam, and lorazepam), antidepressant medications, sleep aids, and analgesics. These medications will be identified through chart review, and include prescription medications, over-the-counter medications, and non-prescription medications. Following study completion, the participant's medical record will be reviewed and the above medications will be identified as will the date of the prescription.

8 ASSESSMENT OF SAFETY

8.1 SPECIFICATION OF SAFETY PARAMETERS

All participants consenting to study participation will be provided with the contact information for the PI, who is a licensed clinical psychologists and providers at the Cancer Center. All participants will have access to psychosocial support services available at the Cancer Center.

8.1.1 DEFINITION OF ADVERSE EVENTS (AE)

Adverse event means untoward or unfavorable medical occurrence related to an intervention in humans.

The following are considered to be adverse events:

- Increase in symptoms of depression and/or anxiety directly related to the act of participating in the intervention (i.e., scheduling appointments, additional visits).
- Increase in symptoms of depression and/or anxiety directly related to material presented in the intervention or the guided imagery audio recordings.

- Increases in anxiety and/or depression related to cancer diagnosis, treatment, impact of treatment on functioning and treatment side effects are **not** considered adverse events. Rather this is the general course of anxiety and depression in the context of RT for HNC.

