The control or treatment as usual condition will include an orientation to RT from the clinic nurse coordinator. This will include a tour of the treatment room and education about RT. Patients will also receive educational materials about RT including the process of RT and CT simulation, treatment side effects, pain management, and swallowing exercises. Participants in this condition will also have access to psychosocial support resources (i.e., clinical psychologists and social workers) at UCCC. Patient use of these services during the study period will be monitored through chart review.

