7.3.4 FINAL STUDY VISIT

Following completion of the Week 12 study assessment measures the participant will connect with the study research assistant either in person or by telephone. Treatment as usual participants

will be provided with an MP3 player containing the guided imagery audio files either in person or by mail. Intervention participants will be asked to participate in a 30-minute qualitative interview assessing the acceptability and feasibility of the intervention. This visit, once scheduled, will be the final study visit.

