8.3 TIME PERIOD AND FREQUENCY FOR EVENT ASSESSMENT AND FOLLOW-UP

The PI will record all reportable events with start dates occurring any time after informed consent is obtained until the last day of study participation. At each study visit, the investigator will inquire about the occurrence of any related AEs since the last visit. Events will be followed for outcome information until resolution or stabilization.

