8.5 SAFETY OVERSIGHT

The principal investigator will be responsible for the conduct of this study, overseeing participant safety, executing the data and safety monitoring (DSM) plan, and complying with all reporting requirements to local and federal authorities. This oversight will be accomplished through additional oversight from the Data and Safety Monitoring Committee (DSMC) at the University of Colorado Cancer Center (CU Cancer Center). The DSMC is responsible for ensuring data quality and study participant safety for all trials at the CU Cancer Center. A summary of the DSMC's activities is as follows:

- Conduct of internal audits

- Ongoing review of all serious adverse events (SAEs) and unanticipated problems (UAPs)
- May submit recommendations for corrective actions to the CU Cancer Center's Executive Committee

Per the CU Cancer Center Institutional DSM Plan, SAEs and UAPs are reported to the DSMC, IRB and the principal investigator per protocol. All SAEs and UAPs are to be reported to the DSMC within 7 (for fatal or life-threatening events) or 15 (non-life-threatening events) calendar days of the principal investigator receiving notification of the occurrence.

Study audits conducted by the DSMC will consist of a review of the regulatory documents, consent forms, and source data verification. Documentation of the audit conducted by the DSMC will then need to be submitted to the IRB of record at the time of the IRB's continuing review of this trial.

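### Adverse events are recorded only if attributed to guided imagery, so AE counts give no between-arm safety comparison, and no summary of individual HADS worsening is prespecified

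*Combined protocol and SAP*

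**What the plan says.** **Definition.** Section 8.1.1 states: "Adverse event means untoward or unfavorable medical occurrence related to an intervention in humans". It lists two types of event: "Increase in symptoms of depression and/or anxiety directly related to the act of participating in the intervention" and "Increase in symptoms of depression and/or anxiety directly related to material presented in the intervention or the guided imagery audio recordings". It then takes a third group out. The sentence that begins "Increases in anxiety and/or depression related to cancer diagnosis, treatment, impact of treatment on functioning and treatment side effects are" ends by saying that these do not count as adverse events, because they are the usual course during radiotherapy (RT) for this cancer.

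**Ascertainment.** Section 8.3 applies the same filter to the question asked: "At each study visit, the investigator will inquire about the occurrence of any related AEs since the last visit". Section 4.1 says that neither participants nor investigators can be blinded; only the biostatistician is.

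**Control arm.** Section 6.1 says: "The control or treatment as usual condition will include an orientation to RT from the clinic nurse coordinator". Education and access to psychosocial support complete the condition. Controls receive the audio files only at the final contact (7.3.4): "Following completion of the Week 12 study assessment measures the participant will connect with the study research assistant".

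**Other safety routes.** Section 8.1.2 defines unanticipated problems (UAPs) to include harm from completing the study measures, which can arise in either arm, but the event must be unforeseen or point to a risk greater than was known. Section 8.5 adds: "All SAEs and UAPs are to be reported to the DSMC". The protocol text does not define an SAE.

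**Symptom data.** All participants complete HADS-A and HADS-D at baseline and in Weeks 1, 3, 7 and 12 (7.1, 7.3.3, 7.4). Section 10.3.3 plans t-tests by arm at the end of RT, and repeated-measures or mixed models with a time-by-treatment interaction. Section 10 contains no safety analysis and no count of participants who worsen.

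**The concern.** Whether worsening was caused by the intervention, the disease or RT is hard to judge in one patient. A randomised control group answers that question at group level, provided that events are recorded in both arms without first asking their cause. Here the cause is judged first, by someone who knows the arm, and only events ascribed to guided imagery are kept.

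A report of no adverse events could then mean that none occurred, or that each one was ascribed to cancer or RT. The AE data cannot separate the two. Section 2.1 describes these patients as highly distressed and at raised risk of suicide, and sections 3 and 10.4 say that the results will inform a larger study. An AE count without a comparator could be carried forward as evidence of safety.

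**Working it through.** **1. Can a control participant have an AE?** Set side by side, both listed types in 8.1.1 need contact with the intervention or its material. Controls have neither until after the Week 12 measures (7.3.4). Only the general opening sentence, which speaks of an intervention without naming it, leaves any room. During the assessment period the expected control count is practically 0, whatever happens to those participants.

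**2. What does the plan compare?** Inputs from 10.4: 36 per arm, two-sided alpha 0.05, SD taken as known. Power = Φ(δ / (SD × √(2/n)) − 1.96).
- HADS-A: δ = 6.9 − 3.6 = 3.3 and SD 5.0. The standard error is 5.0 × √(2/36) = 1.179, so Φ(2.800 − 1.960) = 80.0%.
- HADS-D: δ = 11.2 − 7.5 = 3.7 and SD 5.5. The standard error is 5.5 × √(2/36) = 1.296, so Φ(2.854 − 1.960) = 81.4%.

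The stated 80% is reproduced. The comparison of mean symptoms is planned, two-sided and powered for those differences.

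**3. What can a mean hide?** Illustration with assumed figures: of 36 participants, 30 fall by 2 points and 6 rise by 5. The mean change is (30 × (−2) + 6 × 5) / 36 = −30/36 = −0.83. The arm improves on average while 6/36, one in six, get worse.

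**4. What would zero AEs show?** The exact two-sided 95% upper limit for 0 of n is 1 − 0.025^(1/n).
- n = 36: 1 − 0.025^(1/36) = 9.7%.
- n = 25: 1 − 0.025^(1/25) = 13.7%. This assumes that the minimum enrolment of 50 in the synopsis splits evenly.

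**5. How much worsening could be filtered out?** Section 2.1 gives depression of 15% before treatment and 29% over its course. If those rates apply here, the net rise is (0.29 − 0.15) × 36 = 5.0 participants per arm, or 0.14 × 25 = 3.5 at the minimum enrolment. These are prevalences, so this is a net change. New cases would be more numerous if some baseline cases remit. Under 8.1.1 such worsening could be left out of the AE record by attribution.

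**6. Could the proportion worsened be tested?** Only for large effects. If the control proportion is assumed to be 15%, 29% or 47%, 36 per arm gives 80% power for a rise to about 45%, 61% or 79%.

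**The case against.** The strongest reply is that psychological harm is already compared by randomised arm. HADS is collected on the same schedule in both arms, the tests are two-sided and so can show harm, and a difference in the course of depression is itself a stated hypothesis (10.1). Anxiolytic use is tracked and tested by arm (10.3.7), and antidepressants and sleep aids are recorded from the chart (7.5). A reader might infer from the AE definition that worsening cannot be compared between arms, or that randomisation is not used to assess it. The documents do not support either reading.

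A reader might also say that controls can have no safety event at all. That is too strong, because the UAP and SAE routes are open to both arms. They do not replace the missing comparison, however. The protocol already foresees that reflecting on psychological states can be upsetting (2.3, 2.3.1), so ordinary distress of that kind would seldom qualify as unforeseen.

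Three further points stand. The 9.7% limit comes from the sample size, not from the AE definition. The 15% and 29% rates are not the only guide: the control HADS-D mean of 11.2 (SD 5.5) in 10.4 would, under normality, put roughly 72% to 75% of controls at or above 8 at the end of RT, so the figure of 5 per arm is an illustration and not a forecast. And this is a single-site, minimal-risk pilot with a feasibility endpoint that disclaims conclusions on effectiveness.

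What the reply does not meet is that the planned HADS analyses are of group scores, and that the AE count passes through an unblinded judgement and has no control rate.

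**Conclusion.** The point holds in a limited form. AE recording is confined to events that unblinded staff attribute to the intervention. The control arm has practically no route to an AE, so AE counts cannot give a between-arm safety comparison. Mean HADS scores are compared, but individual worsening is not summarised in any prespecified way.

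In size: zero AEs in the guided imagery arm would leave a true rate of up to 9.7% open (13.7% at 25 per arm), with no control rate beside it. A net rise of about 5 of 36 depression cases per arm, if the rates in 2.1 apply, could be left out by attribution. That all of it would be left out is a worst case, not a prediction.

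No primary or secondary analysis is affected. This is a cheap improvement to consider, not a flaw that undermines the trial.

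**What to change.** **Sections 8.1.1 and 8.3.** Record every participant-reported increase in anxiety or depression in both arms regardless of cause, and enter the judgement of attribution in a separate field. Ask both arms the same question, in the same way and on the same schedule. The last point matters because guided imagery participants have two therapist sessions that controls do not, and measures are mainly completed online, so inquiry tied to visits may differ by arm. SAE and UAP reporting can stay as it is.

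**Section 10.3.** Add one descriptive table by arm at each post-baseline HADS visit (Weeks 1, 3, 7 and 12), separately for HADS-A and HADS-D:
- the number newly at or above the protocol's cut score of 8, among those below 8 at baseline;
- the number whose score rose from baseline;
- the denominator for each.

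**Cost.** Revised wording in two sections, a little more recording in the control arm, and one table from data already collected. The sample size does not change. At 36 per arm the table is descriptive, not a powered test. It puts a control figure beside the guided imagery figure, and does not make either more precise.

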8.1.2 DEFINITION OF UNANTICIPATED PROBLEMS (UAP)

This study will use the COMIRB definition of UAP.

- Any event or information that was unforeseen and indicates that the research procedures (i.e., participation in intervention or completion of study measures) caused harm (including physical, psychological, economic, or social harm) to participants or others or indicates that participants or others are at increased risk of harm than was previously known or recognized.

8.2 CLASSIFICATION OF AN ADVERSE EVENT

8.2.1 SEVERITY OF EVENT

For AEs not included in the protocol-defined grading system, the following guidelines will be used to describe severity.

- Mild** – Events require minimal or no treatment and do not interfere with the participant's daily activities.
- Moderate** – Events result in a low level of inconvenience or concern with the therapeutic measures. Moderate events may cause some interference with functioning.
- Severe** – Events interrupt a participant's usual daily activity and may require systemic drug therapy or other treatment. Severe events are usually potentially life-threatening or incapacitating.

8.2.2 EXPECTED ADVERSE EVENTS

[name] will be responsible for determining whether an AE is expected or unexpected. An AE will be considered unexpected if the nature, severity, or frequency of the event is not consistent with the risk information previously described for the study intervention.

8.3 TIME PERIOD AND FREQUENCY FOR EVENT ASSESSMENT AND FOLLOW-UP

The PI will record all reportable events with start dates occurring any time after informed consent is obtained until the last day of study participation. At each study visit, the investigator will inquire about the occurrence of any related AEs since the last visit. Events will be followed for outcome information until resolution or stabilization.

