7 STUDY PROCEDURES AND SCHEDULE

7.1 STUDY PROCEDURES/EVALUATIONS

Following consent and completion of baseline measures, the participant will be randomized to either the intervention or treatment as usual condition. The research study assistant will coordinate the scheduling of the two intervention sessions for participants in the GI condition. Administration of the study measures will occur online, via REDCap. Participants will be offered the opportunity to begin/complete the survey at the cancer center on a provided tablet, but may also complete the survey in its entirety at home on their own personal internet-connected device.

All participants will complete assessments at baseline, following initiation of RT (during Week 1 of treatment), approximately halfway through RT (during Week 3 of treatment), at the end of RT (during Week 7 of treatment), and one month following completion of RT (around Week 12 after beginning treatment). Patients may complete the assessments listed any time during the specified week (7 days) of treatment, with Day 1 being defined as the first day of radiation treatment. Each session will also be recorded and reviewed for fidelity to the intervention. Study measures include the following:

- I. Anxiety and depression

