7.3.3 FOLLOW-UP

Participants randomized to the intervention condition will complete two in-person or virtual (telephone or secure videoconference) guided imagery sessions. The first will be during the week of the CT simulation visit and the second during the first week of RT (See Table 1).

Table 1. Intervention schedule

Guided Imagery Session	Time	Session Aims
Session 1	During the week of CT simulation	
 • Introduction to guided imagery • Selection of guided imagery vignette • In-session delivery of vignette • Planning for use of guided imagery
Session 2	During first week of RT	
 • Review of guided imagery use • Selection of new vignette if necessary • Addressing barriers to guided imagery use

Patients will then be able self-administer the GI both before and during RT throughout their treatment. Follow-up data for all participants will be collected during the third week (or halfway point) of RT, following completion of RT, and approximately one month following completion of RT. All participants will complete weekly self-assessment of anxiolytic medication use. Intervention participants will complete weekly assessments of guided imagery intervention use. See Table 2 below for schedule of data collection.

Table 2. Assessment schedule for study participants

Construct	Measure	Baseline & Prior to RT	Week 1	Week 2	Week 3	Week 4	Week 5	Week 6	Week 7	Week 12
Anxiety	HADS-A	X	X		X				X	X
Depression	HADS-D	X	X		X				X	X
Symptoms	MSAS-SF	X			X				X	X
Health-related QOL	FACT-HN	X			X				X	X
Intervention use*	TLFB-I	X	X	X	X	X	X	X	X	
Anxiolytic use	TLFB-A	X	X	X	X	X	X	X	X	
Demographics		X								

* Guided imagery participants only

HADS-A = Hospital Anxiety and Depression Scale – Anxiety Subscale; HADS-D = Hospital Anxiety and Depression Scale – Depression Subscale; MSAS-SF = Memorial Symptom Assessment Scale – Short Form; FACT-HN = Functional Assessment of Cancer Therapy – Head and Neck Version; TLFB-I = timeline follow-back for intervention use; TLFB-A = timeline follow-back for anxiolytic use

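### AE inquiry depends on an undefined study visit, so Weeks 2–7 of guided imagery self-use have no scheduled AE question

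*Combined protocol and SAP*

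**What the plan says.** Section 8.3 requires reportable events to be recorded if they start "any time after informed consent is obtained until the last day of study participation". To find them it provides one active step: "At each study visit, the investigator will inquire about the occurrence of any related AEs since the last visit". The term study visit is not defined anywhere in the protocol.

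Section 8.1.1 names two kinds of AE. Both are increases in anxiety or depression attributed to the study: one to the act of taking part in the intervention, the other "directly related to material presented in the intervention or the guided imagery audio recordings". Increases due to the cancer or its treatment are expressly excluded.

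On contacts, section 7.3.3 gives the GI arm two sessions: "The first will be during the week of the CT simulation visit and the second during the first week of RT". In the 7.4 table the row "In-Person or virtual GI Session" is marked only in those two columns. Exposure then continues without staff: "Patients will then be able self-administer the GI both before and during RT throughout their treatment". For questionnaires, section 7.1 states: "Administration of the study measures will occur online, via REDCap", and allows the whole survey to be done at home. Section 7.3.4 describes the next contact planned for everyone: "Following completion of the Week 12 study assessment measures the participant will connect with the study research assistant either in person or by telephone". That section calls this contact the final study visit.

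**The concern.** The AE rule and the schedule do not fit together. The rule assumes visits at which someone asks. After Week 1 the schedule consists of online forms until the closing contact. Self-use of the recordings is the main continuing exposure, and distress from the recordings is one of the two AE types the protocol names, yet for most of that period nobody is scheduled to ask about it.

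Two things are at stake. First, section 5.5 lets study personnel suspend participation they believe is harmful, and the reporting clocks in 8.4.2 and 8.5 start when the investigator learns of an event. Both depend on timely information. Second, the pilot is meant to inform larger studies. Asking at the end whether distress weeks earlier came from the recordings or from radiotherapy gives weak safety data.

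**Working it through.** The plan states no figure on this point, so the check compares the schedule with the AE rule and counts days.

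**Contacts planned for everyone in the arm**

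| Period | GI arm | Control arm |
|---|---|---|
| Screening/baseline (7.3.1, 7.3.2) | Study staff | Study staff |
| CT simulation week (7.3.3, 7.4) | Session 1, therapist | Clinical appointment; no study-staff contact described |
| RT Week 1 | Session 2, therapist | Online forms |
| RT Weeks 2–7 | Online forms | Online forms |
| After Week 12 measures (7.3.4) | Research assistant | Research assistant |

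**Day count.** Sections 7.1 and 7.4 set Day 1 as the first radiation day, so Week *n* runs from Day 7(*n* − 1) + 1 to Day 7*n*.

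- Session 2 (Week 1): Days 1 to 7.
- Week 2 starts on Day 8; Week 7 ends on Day 49.
- Week 12: Days 78 to 84.

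**Gap in the GI arm from Session 2 to the final contact, if that contact falls in Week 12**

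- Shortest: 78 − 7 = 71 days.
- Longest: 84 − 1 = 83 days.

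The contact follows completion of the Week 12 measures, so it may come later and the gap may be longer.

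**Share of marked self-use without a staff-led contact.** Table 7.4 marks self-use in Weeks 1 to 7. Weeks 2 to 7 are 7 − 1 = 6 of those 7 weeks.

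**Delay before an event in Weeks 2–7 is asked about, same assumption**

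- Event on Day 49, contact on Day 78: 78 − 49 = 29 days.
- Event on Day 8, contact on Day 84: 84 − 8 = 76 days.

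**Controls.** From RT Day 1 to the start of Week 12 is 78 − 1 = 77 days. The interval from baseline to RT must be added, and the documents do not state it.

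**Could the other data in the gap do the job?** Every participant has two questionnaire points (Weeks 3 and 7) and six weekly time line follow-back (TLFB) links in Weeks 2–7.

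- HADS can show that symptoms rose. The 8.1.1 definition turns on why they rose, and HADS does not ask. No section attaches an alert or review to a HADS score.
- TLFB records medication use and, in the GI arm, intervention use. Staff telephone only those who do not return it (4.2.3, 7.1), and only to administer the recall.
- Clinic-tablet or telephone completion of assessments (5.3) is optional.
- The early termination contact (7.3.5) reaches only those who withdraw.
- The PI contact details given to all participants (8.1) allow spontaneous reports, not inquiry.

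None of these puts an AE question to every participant between Week 1 and the final contact.

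**The case against.** The strongest reply is that the defect is an undefined term, not a proven absence of inquiry. Weeks 3 and 7 could be read as study visits. Section 5.3 says the research assistant stays in touch with participants and coordinates assessment sessions, and operational detail may sit in the monitoring plan or procedures manual, which are not available here. The protocol rates risk as minimal, and all participants have access to psychosocial support. This is fair. It limits the point to what the protocol itself schedules, but if Weeks 3 and 7 are meant as visits, the protocol should say so and say who asks.

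Four stronger readings are tempting, and the documents do not support them.

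- *The whole of home use goes unasked.* Under 6.1 the recordings are handed over after Session 1, so home use starts before Session 2. Session 2 includes a review of use. The uncovered part begins after it.
- *Every event is found about 11 weeks late.* The final contact asks back to the last visit, so the period is covered retrospectively. For events in Weeks 2–7 the delay is 29 to 76 days if that contact falls in Week 12; 11 weeks is roughly the maximum.
- *Controls go at least 12 weeks without inquiry.* This needs the pre-RT interval, which is not given. The CT simulation column in 7.4 is also not limited to the GI arm, although no study-staff contact with controls is described there.
- *Unequal inquiry biases a comparison of the arms.* Section 10 plans no AE comparison. The named AEs concern an intervention whose recordings controls receive only after Week 12.

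The mismatch of roles is minor. Section 8.3 assigns the question to the investigator, while a therapist runs the sessions and the research assistant makes the last contact. Delegation under the PI is normal, but it should be written down.

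**Conclusion.** The point holds as a gap in contemporaneous AE inquiry. As written, the schedule has no staff-led contact for every participant from Session 2 until after the Week 12 measures: 71 to 83 days, or longer if the last contact is late. Six of the seven weeks marked for self-use fall in that gap. Related distress in those weeks can still be picked up by spontaneous report, incidental contact or recall, but no one is scheduled to ask at the time.

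This assumes that a study visit means a contact with study staff, that online forms are not visits, and that no unseen operational document adds an inquiry. Given the minimal risk the protocol describes, this is a worthwhile low-cost correction. It does not show that participants are unsafe or that any planned analysis is biased.

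**What to change.** In 8.3, replace the general reference to visits with named inquiry points and a named person at each: the therapist at the two GI sessions and the research assistant at the final contact, both reporting to the PI.

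Add one AE item, worded identically in both arms, to the REDCap surveys already sent: the weekly anxiolytic TLFB in Weeks 1–7 and the Week 3, 7 and 12 assessments. It should ask about new or worse anxiety or low mood that the participant relates to study materials or procedures, with free text. A question about distress in general would mostly collect what 8.1.1 says is not an AE. Positive answers go to the PI for classification under 8.1 and 8.2. Add an AE row to 7.4 so that 7.1, 7.3.3, 7.3.4, 7.4 and 8.3 agree.

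The cost is a small amendment, one REDCap item with a notification, a slightly longer survey, and PI time to review positive answers, some of them unrelated to the study. No new scheduled contact is needed. Capture will remain incomplete: 7.4 lets TLFB be completed at any time, and 14.3 does not treat missed or late surveys as deviations when the forms were sent properly. No survey is scheduled in Weeks 8–11, so events in those weeks would still wait for the Week 12 question.
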